### **7.1. Inclusion criteria**

1. Patient who agrees to participate in the study by signing the informed consent.
2. Men and women (non-pregnant) aged  $\geq 18$  years.
3. PCR-confirmed COVID-19 infection obtained from nasopharyngeal exudate or sample from the lower respiratory tract.
4. Patients who require hospitalisation for COVID-19
5. Onset of symptoms no later than 10 days prior to study inclusion.
6. Men and women with reproductive capacity must agree to use highly effective contraceptive methods (diaphragm plus spermicide or male condom plus spermicide, oral contraceptive combined with a second method of contraceptive implant, injectable contraceptive, permanent intrauterine device, sexual abstinence or vasectomy) during their participation in the study and in the 6 months following the last administration of plitidepsin.
7. In addition, women participating in the study with reproductive capacity must have a negative pregnancy test at enrolment.

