  - 9 The first time the patient tested positive for COVID-19 will be included as well. The test will be repeated in the 48 hours prior to administration of plitidepsin and on days 4, 7, 15 and 31, if negative detection does not occur before then. Qualitative PCR shall be obtained on nasopharyngeal exudate (preferably) or a sample from the lower respiratory tract.
  - 10 A chest X-ray will be performed at baseline and subsequently based on clinical discretion.
  - 11 Only fertile women.
  - 12 Patients may receive other pharmacological treatments for COVID-19 at the discretion of the investigator 24 hours after administration of the last dose of plitidepsin.
  - 13 Adverse events (serious and non-serious) will be recorded from signing of the informed consent up to 28 days after administration of the last dose of plitidepsin.
  - 14 A safety visit will be made 28 days (+3 days) after the last dose of plitidepsin.
  - 15 The viral load should be determined in a sample obtained from nasopharyngeal exudate (preferably) or a sample from the lower respiratory tract.

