## **12.5. Analysis of secondary endpoints**

### **12.5.1. Efficacy assessments**

Efficacy analyses will be performed on the efficacy population defined above. For the evaluation of efficacy endpoints, the following analyses will be carried out separately for each dosage level:

- The evolution of the viral load from the baseline visit on days 3, 4, 7, 15 and 31 will be provided.
- The time to negative detection of COVID-19 by PCR will be calculated as the time that elapses in days from the date of randomisation to the first date of PCR with a negative result. The time to negative detection will be analysed following the Kaplan-Meier methodology, providing the median and the corresponding 95% confidence interval.
- The number and percentage of patients who die 7, 15 and 31 days after starting the treatment with plitidepsin shall be described.
- The number and percentage of patients who require mechanical ventilation and/or ICU admission at 7, 15 and 31 days will be provided.
- The number and proportion of patients requiring invasive mechanical ventilation shall be stated.
- The number and proportion of patients requiring non-invasive mechanical ventilation shall be stated.
- The number and proportion of patients requiring oxygen therapy shall be stated.

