8.1 Efficacy evaluation

The following tests will be performed to evaluate the efficacy of the treatment:

a) Viral load evolution:

For the analysis of the evolution of the viral load, the number and percentage of patients from who a sample has been collected will be indicated to determine the viral load at baseline and at visit 4, 7, 15 and 31 describing the results in those patients (number of RNA copies detected and log of the number of copies). The result will be given to three decimal places.

The graphs of the evolution of the viral load (mean and median) of the patients from the baseline to the last visit will be presented. These graphs will be shown by separate for each dose level, by FDA baseline classification and Oxygen support or not on day 1.

In addition, the following variables will be analyzed:

- The number and percentage of patients who viral load result is maintained, decreased or increased with respect to the previous visit on days 4, 7, 15 and 31 will be presented.
- Negative detection (global and by dose level):
- The number and percentage of patients with negative or undetectable viral load on days 4,7,15 and 31.
- The number and percentage of patients with negative or undetectable viral load on days 4,7,15 and 31 in the subgroups of low, medium and high initial viral load.
- Time to negative detection (viral load 0 or undetectable) in overall patients from date of PCR at baseline.
- Time to negative detection (viral load 0 or undetectable) based on baseline viral load (high (>7 copies/mL) / medium [4-7 copies/mL] / low (<4 copies/mL)) and other baseline characteristics (sex, age, race, ...) will be explored.
- Time to negative detection based on corticosteroid treatment (<10 days vs > 10 days)
- Viral load (high, medium, low) will be correlated with study outcome variables such as need for oxygen therapy, admission to ICU (Yes / No), NIMV, IMV, days of hospitalization, death (Yes / No).

- Determine the relationship between the number of days with symptoms and having a higher or lower viral load.
- Determine the relationship between viral load and the baseline situation of the patient, mild-moderate-severe, oxygen need / no need.
- The relationship between viral load and different inflammatory parameters (LDH, ferritin, C-reactive protein, D-dimer and lymphocytes) will be graphically analyzed.
- The mean change in viral load log₁₀ RNA copies/mL from baseline to day 4, 7, 31 will be analyzed in:
 - All patients

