 - Moderate and Mild Patients following the FDA Classification
 - Moderate patients following the FDA Classification

b) COVID-19 evolution by PCR:

For the analysis of COVID-19 evolution by PCR, the number and percentage of patients who have taken the PCR test will be indicated at the baseline and at visit 4, 7, 15 and 31 describing the results (positive / negative) in those patients.

A list of PCR evolution of the patients from baseline to the last visit will be presented.

c) Time to negative detection of COVID-19 detection by PCR:

The time to negative detection of the detection of COVID-19 by PCR is defined as the time, in days, from the date of baseline PCR to the first PCR date with a negative result and does not have a positive result in the following PCR or having a negative result in the last PCR date (Day 31).

The following analyses will be presented.

The time to negative detection will be analyzed by the Kaplan-Meier method and the median and the 95% confidence interval will be provided.

- The number and percentage of patients with qualitative PCR at 4, 7, 15 and 31 days
- A descriptive table will be provided in which both variables are related to each of the variables indicated below:
 - Chronic lung disease (excluding asthma) (Yes; No).
 - Oxygen therapy on day 1 (Yes; No).
 - Plitidepsin dose
 - Days from symptoms until 1st dose of plitidepsin
 - Baseline severity of the disease
 - Age
 - Sex
 - Use of corticosteroids
 - Race
 - Use of other antivirals or other specific treatments for COVID 19

d) Deaths:

The number and percentage of patients who die within 7, 15 and 31 days after starting the treatment with plitidepsin will be described.

- From day 1 to day 7
- From day 8 to day 15
- From day 16 to day 31

In addition, cumulative table will be presented with the following groups:

- From day 1 to day 7
- From day 1 to day 15
- From day 1 to day 31

e) Oxygen therapy:

The number and percentage of patients requiring oxygen therapy on days 7, 15 y 31 after the start of plitidepsin treatment.

- From day 1 to day 7
- From day 8 to day 15
- From day 16 to day 31

In addition, cumulative table will be presented with the following groups:

- From day 1 to day 7
- From day 1 to day 15
- From day 1 to day 31

A descriptive table will be provided in which both variables are related to each of the variables indicated below at 4, 7, 15 and 31 days:

- Chronic lung disease (does not include asthma) (Yes; No).

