APPENDIX III

12 EFFICACY EVALUATION

12.1 Efficacy evaluation

Table 12.1.1 Number of patients with PCR

Number of patients with PCR	Dose Cohort			
	1.5 mg N=X	2.0 mg N=X	2.5 mg N=X	Total N=X
Baseline				
Undetectable				
Positive				
Day ...				

Table 12.1.2 Viral load classification by dose level and total

Day	Viral Load at baseline (copies/mL)	Viral Load classification during treatment (copies/mL)			
		Low <4	Medium [4-7]	High >7	Total
Day 4	Low <4				
	Medium [4-7]				
	High >7				
	Total				
...(*)	Low <4				
	Medium [4-7]				
	High >7				
	Total				

(*) Days 7, 15 and 31

Listing 12.1.3 Viral load evolution

Subject id	Dose	Visit	Result	log10 viral load copies/mL

Table 12.1.4 Summary of Protocol-Specified Efficacy Endpoints. Cumulative results.

Endpoint from day 1 to	Dose Cohort			
	1.5 mg N=X	2.0 mg N=X	2.5 mg N=X	Total N=X
Patients discharged from hospital, n (%)				
Day 7				
Day 8				
Day 15				
Day 31				
Deaths at, n (%)				
Day 7				
Day 15				
Day 31				
Later than Day 31				
Patients requiring invasive mechanical ventilation and/or ICU admission at, n (%)				
Day 7				
Day 15				
Day 31				
Patients requiring invasive mechanical ventilation, n (%)				
Day 7				
Day 15				
Day 31				
Patients requiring ICU admission at, n (%)				
Day 7				
Day 15				
Day 31				
Patients requiring non-invasive mechanical ventilation at, n (%)				
Day 7				
Day 15				
Day 31				
Patients requiring oxygen therapy at, n (%)				
Day 7				
Day 15				
Day 31				
Patients requiring oxygen therapy (high flow) at, n (%)				
Day 7				
Day 15				
Day 31				
Patients requiring oxygen therapy (low flow) at, n (%)				
Day 7				
Day 15				
Day 31				

This table will be also performed by age (<65 vs. ≥65 year old (12.1.4.1)

This table will be also performed by FDA classification (12.1.4.2)

Table 12.1.5 Summary of Protocol-Specified Efficacy Endpoints. Non-cumulative results.

Endpoint	Dose Cohort			
	1.5 mg N=X	2.0 mg N=X	2.5 mg N=X	Total N=X
Patients discharged from hospital, n (%)				
Day 1 to Day 8				
Day 9 to Day 15				
Day 16 to Day 31				
Deaths at, n (%)				
Day 1 to Day 7				
Day 8 to Day 15				
Day 16 to Day 31				
Later than Day 31				
Patients requiring invasive mechanical ventilation and/or ICU admission at, n (%)				
Day 1 to Day 7				
Day 8 to Day 15				
Day 16 to Day 31				
Patients requiring invasive mechanical ventilation, n (%)				
Day 1 to Day 7				
Day 8 to Day 15				
Day 16 to Day 31				
Patients requiring ICU admission at, n (%)				

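### The clearance endpoints are not limited to patients with detectable virus before the first dose, so patients already negative at baseline can count as negative at later visits and as very early events in time to negative

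*SAP*

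**What the plan says.** **Entry.** Protocol 7.1 requires "PCR-confirmed COVID-19 infection obtained from nasopharyngeal exudate or sample from the lower respiratory tract" but sets no date for that test. The same section allows "Onset of symptoms no later than 10 days prior to study inclusion".

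**Baseline swab.** Footnote 9 to the protocol's evaluation calendar treats the first positive and the pre-dose test as separate items: "The first time the patient tested positive for COVID-19 will be included as well", and "The test will be repeated in the 48 hours prior to administration of plitidepsin and on days 4, 7, 15 and 31". The later qualitative tests are done only if no negative has occurred before. No criterion requires the pre-dose repeat to be positive.

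**Population.** The efficacy population (protocol 12.3, SAP 4.1) is defined by three doses and at least two weeks of follow-up, or by stopping treatment because the disease worsened. Baseline virology plays no part.

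**Endpoints.** SAP 8.1 c) runs time to negative PCR "from the date of baseline PCR to the first PCR date with a negative result", provided the next PCR is not positive. Protocol 12.5.1 runs it "from the date of randomisation to the first date of PCR with a negative result". SAP 8.1 a) has a viral-load version for patients overall, and also reports "The number and percentage of patients with negative or undetectable viral load on days 4,7,15 and 31".

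**Baseline negatives.** The shell of "Table 12.1.1 Number of patients with PCR" lists an undetectable row beside a positive row under baseline. The baseline viral-load groups are low (<4), medium (4–7) and high (>7), with none for undetectable.

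**The concern.** A patient who is negative before the first dose cannot convert from positive to negative afterwards. If such patients stay in the clearance analyses, the negative-detection rates and time to negative partly describe baseline status.

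Viral load change and time to negative PCR are named secondary objectives, and the efficacy data are part of the joint judgement on the dose for the phase II/III study. Table 12.1.11 compares time to negative by dose with a Kruskal-Wallis p-value, and Table 12.1.7 shows a mean time to undetectable by dose. With 15 patients per dose, an uneven spread of a few baseline-negative patients could create or hide an apparent dose trend.

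**Working it through.** **No plan figure to reproduce.** The documents state no virological rate, effect size or power. Only the head count can be checked: 3 × (9 + 6) = 45, which agrees.

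**Step 1: follow one patient, undetectable before dosing and afterwards.**
- *Negative-detection rates (Tables 12.1.9 and 12.1.10).* Viral load is scheduled on Days 4, 7, 15 and 31 with no stopping rule. The rate counts status, not conversion, so the patient is negative at each visit. On its face the baseline value falls in the low group.
- *Time to negative PCR, SAP clock.* If the baseline PCR may itself be the first negative, this is an event at time 0. If only later tests count, it is an event at the first visit. If footnote 9 stops testing after a baseline negative, there is no later PCR and the check on the next test has nothing to act on.
- *Time to negative PCR, protocol clock.* A negative swab taken before randomisation gives a negative time.
- *Change in log10 viral load.* The patient does not count as a clearance. Depending on how undetectable is coded, the patient contributes about no change and dilutes the mean, or drops out. SAP 8.1 a) treats negative as a load of 0 or undetectable, log10 of 0 is undefined, no substitute value is given, and SAP 4.6 foresees no imputation.

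**Step 2: negative-detection rate.** With k of N = 15 baseline-negative throughout, and p the rate among baseline-positive patients:

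reported rate = [k + p(15 − k)] / 15, so each such patient adds (1 − p)/15.

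| k of 15 (assumed) | p = 20% | p = 40% |
|---|---|---|
| 0 | 20.0% | 40% |
| 1 | 25.3% | 44% |
| 2 | 30.7% | 48% |
| 3 | 36.0% | 52% |
| 4 | 41.3% | 56% |

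The increment is 0.8/15 = 5.3 points at p = 20% and 0.6/15 = 4.0 points at p = 40%.

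**Step 3: Kaplan-Meier median.** With a fraction f entered at time 0, cumulative clearance is f + (1 − f)F(t), where F is clearance among baseline-positive patients. Tests fall on Days 4, 7, 15 and 31. The median moves from Day 15 to Day 7 once f reaches (0.5 − F(7)) / (1 − F(7)).

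| Assumed F at Days 4/7/15/31 | Threshold f |
|---|---|
| 15/40/70/95% | 0.10/0.60 = 16.7% |
| 10/30/60/90% | 0.20/0.70 = 28.6% |
| 5/25/60/90% | 0.25/0.75 = 33.3% |

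Below the threshold the curve shifts but the median does not.

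**Step 4: mean time to undetectable (Table 12.1.7).** If all 15 patients contribute a time and k of them enter at 0, the mean falls by k/15: 7%, 13%, 20% or 27% for k = 1 to 4. It falls by less if they enter at the first visit.

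**Step 5: chance imbalance.** Three arms of Binomial(15, q) were simulated, taking the largest count minus the smallest.

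| q (assumed) | differ by 2 or more | differ by 3 or more |
|---|---|---|
| 5% | 35% | 8% |
| 10% | 60% | 26% |
| 20% | 76% | 48% |

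**The case against.** The SAP never says outright that baseline-negative patients count as clearances; that follows from silence. SAP 2.6 describes the PCR endpoint as compared with baseline, which favours a post-baseline reading over time 0. The condition on the following PCR removes a baseline negative that is followed by a positive. The undetectable row in Table 12.1.1 may be only a template repeated for every visit. If such patients occur, that table would show how many by dose, and the individual PCR and viral-load listings would show who they are. Safety is the primary objective, the analyses are mainly descriptive, and no virology rule selects the dose.

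Much of this stands, and it limits the point. It does not remove it: disclosing the count leaves the endpoints unchanged, and the post-baseline reading still scores a persistently negative patient as an event at the first visit tested.

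Some stronger readings are tempting but unsupported:
- *Such patients count as clearances in every virological endpoint.* In log10 change they dilute the mean or drop out.
- *A baseline negative shows natural clearance before dosing.* It may be a false-negative swab. Either way it cannot show conversion from a detectable baseline.
- *The median falls steadily with each such patient.* A continuous exponential with median 15 days and 1 to 4 of 15 at time 0 would give 13.5, 11.9, 10.2 and 8.3 days. On the actual visit days that curve has 27.6% cleared by Day 7, so the threshold is (0.5 − 0.276)/(1 − 0.276) = 30.9%, or 4.6 of 15, and the median does not move anywhere in that range.
- *Each such patient adds about 7 points to the negative rate.* That is the upper bound, reached only when p = 0.

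**Conclusion.** The gap is real. Nothing limits the clearance endpoints to patients with detectable virus before dosing, a negative pre-dose swab is possible under the entry rules, and the written definitions count a persistently negative patient in the Day 4 to 31 rates. Time to negative has several readings, none of which measures conversion in that patient.

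The size is unknown because the documents give no count of baseline-negative patients; every range above rests on assumed values. On those assumptions the negative-detection rates and a mean time with time-0 entries are the sensitive summaries. The Kaplan-Meier median is fairly robust. Differences between doses are exposed, since at 15 per arm an imbalance of two or more such patients is likely if about 10% are baseline-negative. This is worth correcting before the final analysis, but it does not touch the primary safety objective.

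**What to change.** In protocol 12.5.1 and SAP 8.1 a) and c):
- Run viral load change, negative-detection rates and time to negative in efficacy patients with a detectable viral load on the last pre-dose sample, or a positive PCR for the PCR endpoint.
- Count only post-dose negatives as events.
- State the log10 value to be used for undetectable results.
- Use one time origin in both documents.
- Report baseline-negative patients by dose in the footnotes of Tables 12.1.7 and 12.1.9 to 12.1.11 and of Figure 12.1.42. Table 12.1.1 already provides the count.
- Keep these patients in the clinical and safety analyses.

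This takes a population flag and changes of wording. The pre-dose sample is already collected, so no new patients or samples are needed. The cost is slightly smaller virology denominators. With no control arm, the restricted analysis still cannot separate a drug effect from natural clearance after dosing, and the report should say so.

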### **6.3.Secondary endpoints**

- Change in SARS-CoV-2 viral load from baseline (day -1 or day 1 before administration of the study drug) measured at days , 4, 7, 15 and 31.
- Time until the detection of COVID-19 by PCR obtained from nasopharyngeal exudate or sample from the lower respiratory tract compared to baseline (day -2 or -1 or day 1 before administration of the study drug).
- Mortality at 7, 15 and 31 days.
- Percentage of patients requiring invasive mechanical ventilation and/or ICU admission at 7, 15 and 31 days.
- Percentage of patients requiring non-invasive mechanical ventilation at 7, 15 and 31 days.
- Percentage of patients requiring oxygen therapy at 7, 15 and 31 days.
- The recommended dose level will be selected after the joint evaluation of the safety and efficacy data obtained in this study between the sponsor and the Spanish Agency of Medicines and Medical Devices.

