### **7.3. Randomisation procedures**

Patients will be randomised, provided patients are included at more than one dose level (arm), in a 1:1 or 1:1:1 ratio as appropriate, once the investigator has confirmed that they meet the selection criteria and the patient has given informed consent.

During the extension period, patients will be randomised in a 1:1:1 ratio as appropriate to each dose level (arm).

The randomisation will be done in blocks.

Randomisation will be done through registration in the study's eCRF. The system will assign a unique randomisation number for each patient. This number should be included in all study documents related to the patient.

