- Total patients requiring ICU (95% IC)
- Number and percentage of patients requiring ICU admission since the start of treatment with plitidepsin.
 - From day 1 to day 7
 - From day 8 to day 15
 - From day 15 to day 31
- In addition, cumulative table will be presented with the following groups:
 - From day 1 to day 7
 - From day 1 to day 15
 - From day 1 to day 31
- A descriptive table in which this variable is related to each of the variables indicated below at 4,7, 15 and 31 days from the start of treatment will be provided:
 - Chronic lung disease (does not include asthma) (Yes; No).
 - Oxygen therapy at baseline (Yes; No).
 - Days from onset of symptoms (continuous)
- Time in ICU admission (continuous): The time in ICU is defined as the time, in days, from ICU admission to ICU discharge. It will be only calculated for those patients who have been admitted and discharged from the ICU.
- Onset day of ICU admission (continuous): Onset day of ICU admission is defined as the time, in days, from the date of the first dose of plitidepsin treatment to the date of admission to the ICU. It will only be calculated for those patients who have been admitted to the ICU.
- Use of corticosteroids and/or antiviral and other specific COVID 19 treatments
- Time from ICU admission to Hospital discharge (continuous): The time from ICU admission is defined as the time, in days, from the date of ICU admission to the date of discharge from the center. It will only be calculated for those patients who have been admitted and discharged from the ICU and have also been discharged from the center. Reason for ICU discharge (taken back to the ward; Death; Others).
- Invasive mechanical ventilation (Yes; No).
- Non-invasive mechanical ventilation (Yes; No).
- High flow oxygen therapy (Yes; No).

k) ICU admission or Mechanical ventilation (Invasive):

The following analysis will be performed:

- Number and percentage of patients requiring invasive mechanical ventilation or ICU admission since the start of treatment.
 - From day 1 to day 7
 - From day 8 to day 15
 - From day 16 to day 31
- In addition, cumulative table will be presented with the following groups:
 - From day 1 to day 7
 - From day 1 to day 15
 - From day 1 to day 31

l) Hospitalization:

The following variables will be analyzed:

- Hospital discharge (Yes / No). If not, a list of reasons will be provided.

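### Time to negative PCR has a different start date and a different event definition in the protocol and the SAP; the SAP clock adds 0 to 2 pre-treatment days

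*SAP*

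**What the plan says.** Protocol 12.5.1 defines the endpoint as "the time that elapses in days from the date of randomisation to the first date of PCR with a negative result". SAP 8.1 c instead measures "from the date of baseline PCR to the first PCR date with a negative result", and adds that the next PCR must not be positive, or that the negative is the one at the last PCR (Day 31). The viral-load version in SAP 8.1 a uses the same start: "Time to negative detection (viral load 0 or undetectable) in overall patients from date of PCR at baseline". The footnote to SAP Table 12.1.7 repeats the baseline PCR as the origin for mean time to undetectable viral load.

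On the timing of swabs, footnote 9 of the protocol's evaluation calendar says: "The test will be repeated in the 48 hours prior to administration of plitidepsin and on days 4, 7, 15 and 31". The endpoint text in protocol 6.3 gives the same window in days.

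On randomisation, protocol 7.3 says: "Patients will be randomised, provided patients are included at more than one dose level (arm". The same section says that the eCRF system gives each patient a randomisation number.

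Elsewhere in 8.1 the SAP starts the clock at treatment. ICU onset runs "from the date of the first dose of plitidepsin treatment to the date of admission to the ICU", and the time-to-event version of hospital discharge runs from treatment start.

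**The concern.** One secondary endpoint has two start dates and two event rules, and nothing in the SAP records a change from the protocol.

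The SAP's start date floats by up to 48 hours relative to first dose, but follow-up PCR is scheduled by treatment day. Two patients who clear at the same visit can therefore receive times up to two days apart because of when the baseline swab was taken. With only four planned follow-up tests, event times should be heavily tied, so this matters for rank-based comparisons. SAP Table 12.1.11 applies Kruskal-Wallis tests to time to negative detection by dose, baseline viral load, age, sex, race and other factors, and 8.1 c reports a Kaplan-Meier median with a 95% confidence interval.

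The protocol's start date has its own difficulty: it is not clear what it means for a patient enrolled while only one dose level is open.

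**Working it through.** **1. The definitions side by side.**

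| Source | Clock starts | Event |
|---|---|---|
| Protocol 12.5.1 | Randomisation | First negative PCR |
| SAP 8.1 c | Baseline PCR | First negative with no positive at the next PCR, or negative at Day 31 |
| SAP 8.1 a, Table 12.1.7 footnote | Baseline PCR | Undetectable viral load |

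**2. Size of the SAP's pre-treatment time.** Protocol 6.1 equates 12 days after the end of treatment with day +15. Treatment ends on Day 3 and 3 + 12 = 15, so Day 1 is the day of first dose.

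Time from first dose = visit day − 1. SAP time = (visit day − 1) + L, where L is the number of days from baseline swab to first dose. The 48-hour window gives L = 0, 1 or 2.

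| Negative at | First-dose clock | SAP clock | Largest addition |
|---|---|---|---|
| Day 4 | 3 | 3 to 5 | 2/3 = 67% |
| Day 7 | 6 | 6 to 8 | 2/6 = 33% |
| Day 15 | 14 | 14 to 16 | 2/14 = 14% |
| Day 31 | 30 | 30 to 32 | 2/30 = 7% |

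The ranges do not overlap (5 < 6, 8 < 14, 16 < 30). With visits on their nominal days, the lag splits ties within a visit but never reverses the order between visits. Each individual time moves by 0 to 2 days, so a median with no censoring before it also moves by 0 to 2 days.

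**3. Patients enrolled while one arm is open.** Using the heading size for the fourth group, the groups in SAP 3.1 sum to 3 + 6 + 9 + 6 + 3 = 27, which reproduces the plan's figure; 27 + 18 = 45. The body text of 3.1.4 says 9 instead of 6, which would give 30 and does not reproduce it.

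The single-arm groups are the first (3 in arm A) and the fifth (3 in arm C): 3 + 3 = 6 under either reading. That is 6/45 = 13.3% overall: 3/15 = 20% in A, 0/15 in B and 3/15 = 20% in C.

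**4. Size of the event-definition difference.** Take a patient who is negative at Day 4, positive at Day 7, and negative at Days 15 and 31. The protocol's event is at Day 4 and the SAP's is at Day 15. From first dose that is 3 versus 14 days, a gap of 11 days, which is much larger than the swab lag.

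Calendar footnote 9 also makes later PCRs conditional on no earlier negative. If testing stops at the first negative, there is no following PCR on which to apply the SAP's rule.

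**The case against.** The SAP's origin is not arbitrary. Protocol 6.3 describes this endpoint as "compared to baseline (day -2 or -1 or day 1 before administration of the study drug", and SAP 2.6 repeats that, so the sentence in protocol 12.5.1 is the outlier. Time from the baseline test is also a coherent quantity that exists for anyone with the scheduled swab. This stands as a reason why the SAP may have chosen it. It does not remove the conflict with 12.5.1 or the variable lag.

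Three stronger readings are tempting, and the documents do not support them.

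- A reader might infer that the protocol endpoint is undefined for six patients. Protocol 7.3 limits randomisation to periods with more than one open arm, yet gives every patient a randomisation number through eCRF registration, and protocol 9.2 and 12.2 write as if all patients are randomised. The origin is unclear, and a registration date could stand in if the plan said so. Six is a planned count inferred from the SAP's sequence; it assumes no arm closures and no replacements.
- A reader might infer that results are inflated by 67%. That is the maximum lag combined with the earliest visit. No lag distribution is given, so the effect on the actual median cannot be derived.
- A reader might infer bias between doses. Nothing suggests that swab timing differs by arm; a lag unrelated to arm adds noise.

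It is also fair that gaps between scheduled PCRs (3, 8 and 16 days) are coarser than a two-day shift, and that the planned proportions negative at Days 4, 7, 15 and 31 do not depend on the baseline swab date.

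**Conclusion.** The concern holds in a limited form. The two documents disagree on both the start and the event for time to negative PCR, and the SAP does not say so. Relative to first dose, the SAP clock adds 0 to 2 days to each patient's time and never subtracts any. It breaks ties that the visit schedule would otherwise create, which affects the Kaplan-Meier estimate and the Kruskal-Wallis tests. The difference in event definition can move an individual time by more than the difference in origin.

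This rests on reading the baseline PCR as the repeat swab in the 48-hour window, and not the first positive test that footnote 9 also records, and on visits at their nominal days. The interval from randomisation to first dose is not stated, so the exact gap between the protocol's clock and the SAP's cannot be computed.

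The impact is modest: the endpoint is secondary, the analysis is mainly descriptive, and the dose is chosen on the joint safety and efficacy evidence.

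**What to change.** In protocol 12.5.1, SAP 8.1 a and c, and the footnote to SAP Table 12.1.7, use one origin: the date of first plitidepsin dose. It exists for every treated patient, matches the follow-up schedule, and is already the SAP's origin for ICU onset and time to discharge.

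State one event definition. Say explicitly whether a negative counts only if it is not followed by a positive, and what applies when no later PCR was taken.

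Record both points in the SAP as changes from the protocol, with the reason. Keep the version counted from the baseline swab as a sensitivity analysis if wanted.

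The cost is wording in two documents and a date calculation. No new data are needed for the change of origin.
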